### **2.3. SCIENTIFIC RATIONALE FOR DESIGN**

To have a high level of evidence, a prospective, randomized, single-blinded, parallel, non-inferiority study was the design selected for this study. A within-subject (ie, split-mouth) design was not included since the product compositions allow spreading to adjacent areas of the mouth.

Vanish™ 5% Sodium Fluoride White Varnish was selected as the comparator product (ie, Control device) for this study since it is a well-known fluoride varnish used as a desensitizing agent, with three previous publications describing its impact on the reduction of DHS when used in a clinical trial.

The primary endpoint for this study will focus on the immediate reduction in DHS in response to a air blast stimulus (ie, the change from before product application to immediately after application), as measured using a VAS (see Section 5.3.1). This timepoint was selected primarily due to the abundance of literature analyzing immediate changes in DHS in response to professionally applied F-containing desensitizing agents (see Section 2.1.2). In addition, the baseline VAS and immediate post-application VAS will be assessed at the same visit, thereby limiting the number of Subjects that may be lost to follow-up prior to collection of data for the primary endpoint.

[figure not shown]
It is hypothesized that Clinpro™ 2.1% Sodium Fluoride Aqueous Solution will be non-inferior to Vanish™ 5% Sodium Fluoride White Varnish in immediately reducing DHS.

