#### **5.3. STUDY ENDPOINT(S)**

##### **5.3.1. Primary Endpoint(s)**

Co-primary endpoints include:

- the change in pain, using a 100-mm VAS from baseline to immediately after application (within 15 minutes post treatment) of test product or comparator.
- the change in pain score from baseline to  $24 \pm 4$  h post-application, using VAS after exposure to air stimulus.

Sensitivity will be assessed using VAS after exposure to air stimulus.

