## 8. STATISTICAL CONSIDERATIONS

### 8.1. PASS/FAIL CRITERIA

The null hypotheses that we seek to reject are that Vanish™ 5% Sodium Fluoride White Varnish has a 15.0 mm higher change from baseline VAS than Clinpro™ 2% Sodium Fluoride Aqueous Solution when measured immediately after application (within 15 minutes post-treatment) or at 24-hours after treatment ( $\pm 4$  hours). The null and alternate hypotheses are described below.

$H_0$ : Vanish™ Varnish changed from baseline – Clinpro™ 2.1% Sodium Fluoride Aqueous Solution change from baseline  $> 15$  mm.

$H_a$ : Vanish™ Varnish changed from baseline – Clinpro™ 2.1% Sodium Fluoride Aqueous Solution change from baseline  $\leq 15$  mm.

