## **8.2. SAMPLE SIZE DETERMINATION**

Twenty-eight hypersensitivity studies were reviewed for difference in treatment effect (change from baseline) of actives and several reported differences between actives in VAS change from baseline of greater than 20 mm. Even with these notable differences, the authors routinely declare all actives effective in treatment of hypersensitivity. This study will use a more conservative non-inferiority margin of 15 mm. A standard deviation for change from baseline at immediately after treatment (within 15 minutes post-treatment) and 24-hours of 20 mm will be used. There is uncertainty in the efficacy difference between treatments as well as the error term. An interim analysis will be conducted at approximately 50% of subject treatment to reassess sample size with no alpha spending required. Ninety-six (96; 48 per arm) total subjects will provide 80% power allowing for a 2 mm difference in efficacy difference between treatments and 2 co-primary endpoints tested. No subjects will be lost to follow-up for the primary time point of immediate hypersensitivity relief, but there may be loss to follow-up for co-primary endpoint of hypersensitivity relief at 24-hours after treatment.

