### **8.4.2. Analysis of Primary Endpoints**

At the final analysis, multiplicity will be controlled through a Hochberg procedure. Ninety-five- percent (95%) confidence intervals will be generated for the difference between treatments

in change from baseline immediately after application and separately for the difference between treatments in change from baseline 24-hours after application using Student's t distribution.

Scenario 1: Neither of the 95% confidence intervals contain 15 mm.

Result: Non-inferiority for both co-primary endpoints will be declared

Scenario 2: Both of the 95% confidence intervals contain 15 mm.

Result: No non-inferiority for either co-primary endpoints will be declared, and all analyses will be informational only.

Scenario 3: One confidence interval contains 15 mm, and the other confidence interval does not contain 15 mm.

The endpoint that does not contain 15 mm has the potential to be declared non-inferior. For this endpoint, as part of the Hochberg procedure, a 97.5% confidence interval will be generated. Non-inferiority for this endpoint will be declared if the new confidence interval does not contain 15 mm.

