#### **8.4.3. Analysis of Secondary Endpoints**

If the null hypotheses are rejected for both co-primary endpoints, the alpha will be passed to test for non-inferiority of Clinpro™ 2.1% Sodium Fluoride Aqueous Solution to Vanish™ Varnish for the various secondary endpoints. Ninety five percent (95%) confidence intervals will be generated for the difference between treatments in change from baseline using the Student's t distribution at each evaluation time. Non-inferiority will be declared if Vanish™ Varnish changed from baseline minus Clinpro™ 2.1% Sodium Fluoride Aqueous Solution change from baseline is less than or equal to 15 mm for each secondary endpoint. There are 3 secondary endpoints. The alpha will be passed sequentially in the order listed in section 5.3.2.

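### The co-primary decision rule in Section 8.4.2 names no side of 15 mm, so read literally it declares non-inferiority when the interval lies wholly above the margin

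*Combined protocol and SAP*

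**What the plan says.** Section 8.1 (Pass/Fail Criteria) is directional. The null hypotheses to be rejected are that Vanish "has a 15.0 mm higher change from baseline VAS than Clinpro™ 2% Sodium Fluoride Aqueous Solution", immediately after application or at 24 hours. The null is written as Vanish change minus Clinpro change above 15 mm, the alternative as 15 mm or less.

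Section 8.4.2 names a Hochberg procedure, two-sided 95% intervals and three scenarios:

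- **Scenario 1:** "Scenario 1: Neither of the 95% confidence intervals contain 15 mm". Both endpoints are declared non-inferior.
- **Scenario 2:** both intervals contain 15 mm. Neither is declared.
- **Scenario 3:** one interval contains 15 mm and the other does not. A 97.5% interval is formed for the latter: "Non-inferiority for this endpoint will be declared if the new confidence interval does not contain 15 mm".

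No scenario names a confidence limit, a side of 15 mm or an order of subtraction.

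Section 8.4.3 does give a direction, but only for the secondary endpoints. Non-inferiority is declared if Vanish change minus Clinpro "change from baseline is less than or equal to 15 mm for each secondary endpoint". It does not say which confidence limit must satisfy this.

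Section 5.3.1 defines the first endpoint as "the change in pain, using a 100-mm VAS from baseline to immediately after application", without a sign. Sections 2.3 and 5.3.3 speak of a reduction, which implies that a positive change means relief, but no section gives the formula.

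**The concern.** An interval can exclude 15 mm in two ways. If it lies wholly below, the null in Section 8.1 is rejected and non-inferiority follows. If it lies wholly above, the data support that null: Clinpro is worse by more than the margin. Section 8.4.2 treats the two alike. In the second case Sections 8.1 and 8.4.2 give opposite answers for the same data.

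The mixed case shows it most plainly. Suppose one interval is wholly below 15 mm and the other wholly above. Neither contains 15 mm, so Scenario 1 declares both endpoints non-inferior. A Hochberg procedure on the Section 8.1 nulls could declare at most the first, and only after the 97.5% step.

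At stake is the primary decision rule of a study meant to support registration. It should give one answer without having to be corrected from another section.

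**Working it through.** **Inputs.** From Section 8.2: margin 15 mm, SD of change 20 mm at both times, 48 per arm, planning difference 2 mm, stated power 80%. From Section 8.4.2: two-sided 95% and 97.5% intervals based on Student's t. Assumed, because the documents do not give them: the correlation between the two endpoints (0, 0.4, 0.8) and the true deficits other than 2 mm.

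**The plan's own figure.**
- SE = 20 × √(2/48) = 4.08 mm, with 94 degrees of freedom.
- Distance to the margin = 15 − 2 = 13 mm; noncentrality = 13 / 4.08 = 3.18.
- At one-sided 0.0125, the strictest Hochberg step, noncentral-t power is 81.6%, which agrees with the stated 80%.

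This confirms the inputs. It does not show which reading was intended, because at 2 mm the upper tail contributes practically nothing.

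**Where the fault acts.**

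| Interval | t | Half-width (mm) | Wholly below 15 if observed difference is under | Wholly above 15 if observed difference is over |
|---|---|---|---|---|
| 95% | 1.986 | 8.11 | 15 − 8.11 = 6.89 | 15 + 8.11 = 23.11 |
| 97.5% | 2.278 | 9.30 | 15 − 9.30 = 5.70 | 15 + 9.30 = 24.30 |

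For example, an observed difference of 26 mm gives a 95% interval of 17.9 to 34.1 mm, which Scenario 1 counts towards non-inferiority.

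**How often, same true deficit on both endpoints.** Full three-scenario rule, 400,000 simulated trials per setting, bivariate normal data, pooled variances. Entries are the chance that a given endpoint is declared non-inferior, at correlation 0 / 0.4 / 0.8.

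| True deficit | Literal rule | Upper-limit rule |
|---|---|---|
| 15 mm | 2.6 / 2.8 / 3.3% | 1.3 / 1.4 / 1.6% |
| 20 mm | 16.8 / 17.6 / 18.9% | 0.03 / 0.03 / 0.04% |
| 25 mm | 64.4 / 63.9 / 63.9% | 0% |
| 30 mm | 95.2 / 94.9 / 94.5% | 0% |

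At exactly 15 mm, the chance of at least one declaration is 5.0 / 4.9 / 4.4% under the literal rule and 2.5 / 2.4 / 2.2% under the upper-limit rule.

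**How often, different deficits.** Chance that both endpoints are declared non-inferior:
- 20 mm and 2 mm: literal 20.2 / 17.5 / 13.7%; upper-limit 0.06 / 0.08 / 0.08%.
- 25 mm and 2 mm: literal 59.9 / 57.6 / 56.3%; upper-limit about 0.

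**At the planned difference.** With 2 mm on both endpoints, both are declared in 78.0 / 80.0 / 83.3% of trials under either rule.

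**Order of subtraction and sign.** Section 8.4.2 gives neither. If the difference were formed as Clinpro minus Vanish, a true 15 mm Clinpro deficit would centre the interval at −15 mm. That is 30 / 4.08 = 7.3 standard errors from +15, so the interval would almost always exclude 15 mm. If change were taken as follow-up minus baseline, the relevant bound for Vanish minus Clinpro would be −15 mm.

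**The case against.** The strongest reply is that the documents already supply the direction. Section 8.1 carries the pass/fail heading and fixes both the subtraction and the side. Section 8.4.2 opens with Hochberg, which works on p-values for stated nulls; an interval wholly above 15 mm gives a p-value near 1 for the Section 8.1 null, so nothing could be rejected. Section 8.4.3 describes the co-primary success condition as rejection of both nulls. On this view the scenarios are shorthand, and no statistician would declare non-inferiority on an interval wholly in Vanish's favour. The rates above also need a true deficit of 20 mm or more, against a planning value of 2 mm.

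Much of this stands. The intent can be inferred, a two-sided test was not planned, and the rates are conditional, not expected error rates. Section 8.2 notes that "several reported differences between actives in VAS change from baseline of greater than 20 mm", but does not say how many exceeded 23 mm or between which products. Deficits of 25 to 30 mm are illustrative: two of the three 5% varnish VAS results in Section 2.1.2.2 show total reductions of only about 25 mm (5.9 to 3.4 cm) and 28 mm (58.18 to 30.5 mm).

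What does not stand is that nothing needs changing. Neither the Hochberg sentence nor Section 8.4.3 states a side for the co-primary rule, and the explicit rule that would be applied gives the wrong answer for some results.

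**Conclusion.** The concern holds. As written, Section 8.4.2 declares non-inferiority for any co-primary interval wholly above 15 mm, against the hypotheses in Section 8.1. It is a drafting fault in the primary decision rule. It should be fixed, but it is not a flaw in the design.

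It takes effect only if the observed difference exceeds about 23.1 mm (95% interval) or 24.3 mm (97.5% interval). These thresholds assume 48 per arm and SD 20 mm, and would move if the planned re-estimation changed the sample size. The error rates also depend on the assumed deficits and correlations. Sample size and planned power are unaffected.

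**What to change.** In Section 8.4.2, define the difference as Vanish minus Clinpro and replace the three scenarios with:

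1. If the upper limits of both two-sided 95% intervals are below 15 mm, declare non-inferiority for both endpoints.
2. If only one is below 15 mm, declare that endpoint non-inferior only if the upper limit of its two-sided 97.5% interval is also below 15 mm.
3. Otherwise declare neither.

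In Section 8.4.3, state the same criterion: upper limit of the two-sided 95% interval below 15 mm. In Sections 5.3.1 and 8.1, write out the sign already implied: change = baseline VAS minus post-treatment VAS, so that a positive value means relief.

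The cost is wording in four sections, plus whatever approval and training Section 9 requires for a modification. No extra patients or data are needed, and sample size and planned power do not change. It is best done before any results by treatment arm are seen, so that the correction cannot be called post hoc.

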#### **8.4.3. Analysis of Secondary Endpoints**

If the null hypotheses are rejected for both co-primary endpoints, the alpha will be passed to test for non-inferiority of Clinpro™ 2.1% Sodium Fluoride Aqueous Solution to Vanish™ Varnish for the various secondary endpoints. Ninety five percent (95%) confidence intervals will be generated for the difference between treatments in change from baseline using the Student's t distribution at each evaluation time. Non-inferiority will be declared if Vanish™ Varnish changed from baseline minus Clinpro™ 2.1% Sodium Fluoride Aqueous Solution change from baseline is less than or equal to 15 mm for each secondary endpoint. There are 3 secondary endpoints. The alpha will be passed sequentially in the order listed in section 5.3.2.

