#### **8.4.4. Analysis of Additional/Exploratory Endpoints**

Ninety five percent (95%) confidence intervals will be generated for the difference between treatments in change from baseline using a Student's distribution at each evaluation time. No non-inferiority will be declared.

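### The secondary non-inferiority rule in 8.4.3 compares the difference itself, not its upper confidence limit, with 15 mm; taken literally, an endpoint truly at the margin passes 50% of the time instead of 2.5%, before the co-primary gate.

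*Combined protocol and SAP*

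**What the plan says.** All references are to the combined protocol and SAP.

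- **8.4.3 (secondary endpoints).** Once both co-primary nulls are rejected, alpha passes to the secondary endpoints. At each time, 95% "confidence intervals will be generated for the difference between treatments in change from baseline". Non-inferiority is then declared if the Vanish change minus the Clinpro "change from baseline is less than or equal to 15 mm for each secondary endpoint". The order is fixed: "The alpha will be passed sequentially in the order listed in section 5.3.2", that is, day 7, then 21, then 30.
- **8.4.2 (co-primary endpoints).** The decision is made on the intervals: "Scenario 1: Neither of the 95% confidence intervals contain 15 mm" leads to non-inferiority on both.
- **8.4.4 (exploratory endpoints).** The same kind of interval is produced, followed by "No non-inferiority will be declared".
- **8.1.** Under the null, Vanish "has a 15.0 mm higher change from baseline VAS than" Clinpro. The alternative puts the difference at or below 15 mm.
- **8.2.** "This study will use a more conservative non-inferiority margin of 15 mm". For the SD of change at the immediate assessment and at 24 hours, "24-hours of 20 mm will be used". The sample size is 96 (48 per arm), for 80% power at a true 2 mm difference with two co-primary endpoints.

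Appendix A repeats the 8.4.3 sentence as the updated version 2 text, so it is not an extraction fault.

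**The concern.** The interval in 8.4.3 is calculated but given no part in the decision. The only sentence that declares non-inferiority compares a difference with 15 mm and names no limit. A programmer who followed it literally would compare the observed difference with the margin. That test ignores sampling error and spends no alpha, although the section passes alpha from one endpoint to the next. The adjacent section 8.4.2 uses a different criterion for the same kind of claim.

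Each of the day 7, 21 and 30 endpoints can yield a formal non-inferiority declaration, in a study whose purpose (5.1) is to support an indication and global registration. Once the co-primary gate is passed, the literal rule gives those declarations no error control. The wording also leaves room to choose the reading after the data are seen, over the range of results where the two readings disagree.

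**Working it through.** **Inputs.** Margin 15 mm, SD 20 mm, 48 per arm, true difference 2 mm, two co-primaries (8.2); two-sided 95% intervals, so 2.5% one-sided (8.4.3). Three assumptions are needed:

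- The SD of 20 mm, stated only for the immediate and 24-hour assessments, carries over to days 7, 21 and 30.
- The between-visit correlation, which is not given, lies between 0 and 0.9 and is equal across visits.
- The co-primary rule of 8.4.2 is applied as an upper-limit test.

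**1. The plan's own figure.** The distance from true difference to margin is 15 − 2 = 13 mm. With one-sided alpha 0.0125 (0.025 split over two co-primaries), the t-based calculation needs 47 per arm for 80% power. At 48 per arm the power is 81.6%. The stated 96 is reproduced, and it comes from a confidence-limit test.

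**2. Standard error and critical value.** SE = 20 × √(2/48) = 4.082 mm. t(0.975, 94 df) = 1.9855. Half-width = 1.9855 × 4.082 = 8.11 mm.

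**3. The two rules, before the gate.**

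- Literal: P(observed difference ≤ 15) = Φ((15 − true)/4.082).
- Upper limit: P(observed difference + t × estimated SE < 15), from the noncentral t with 94 df.

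| True difference | Literal | Upper limit |
|---|---|---|
| 2 mm | 99.9% | 88.3% |
| 15 mm | 50.0% | 2.5% |
| 18 mm | 23.1% | 0.36% |
| 20 mm | 11.0% | 0.08% |

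At 15 mm the literal argument is zero, so Φ(0) = 50% whatever the SD or sample size. The upper-limit rule gives 2.5% there by construction.

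**4. Where the readings disagree.** The upper-limit rule needs an observed difference below 15 − 8.11 = 6.89 mm. From there to 15 mm the literal rule declares non-inferiority and the upper-limit rule does not. The lower edge of this band moves as follows:

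- 6.4 mm with 43 per arm (about 10% dropout) and 5.9 mm with 38 per arm (about 20%), SD 20 mm.
- 8.9 mm with SD 15 mm and 4.9 mm with SD 25 mm, 48 per arm.

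**5. After the co-primary gate.** Simulation of 200,000 trials per setting, with co-primaries truly at 2 mm and days 7, 21 and 30 all truly at 15 mm. Percentages are of all trials; day 21 and day 30 also require the earlier secondary endpoints to pass.

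| Correlation | Gate passed | Day 7 literal | Day 21 literal | Day 30 literal |
|---|---|---|---|---|
| 0 | 78.2% | 39.2% | 19.5% | 9.8% |
| 0.3 | 79.4% | 43.6% | 27.2% | 18.4% |
| 0.5 | 80.6% | 46.1% | 32.0% | 24.4% |
| 0.7 | 82.2% | 48.6% | 37.0% | 30.9% |
| 0.9 | 84.9% | 49.9% | 42.7% | 39.1% |

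With the upper-limit rule, day 7 is declared in 2.0% to 2.5% of trials. If the co-primaries are also truly at 15 mm, the gate holds a literal-rule day 7 claim to between 0.04% and 1.45%.

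**The case against.** The strongest reply is that nobody meant a point-estimate rule. The sentence does not say observed or estimated. It nearly repeats the alternative hypothesis in 8.1, which concerns the true difference. It follows a sentence about 95% intervals and sits among sentences about passing alpha, which a point-estimate rule would make pointless. Section 8.4.4 denies any declaration from the same kind of interval, which implies that the secondary intervals are there to support one.

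Appendix A adds evidence. The superseded version 1 primary rule had the same construction and was powered at 92% (no difference) and 83% (2 mm deficit) with 40 per arm. An upper-limit test gives 91.8% and 82.8% by normal approximation at one-sided 0.025; a point-estimate rule would give 99.96% and 99.8%. This is strong evidence of intent, but it does not put a limit into the current sentence. The level 2 validation in 8.8 would not necessarily catch the problem, because a point-estimate program conforms to the text.

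Two further points stand in part:

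- **Section 8.4.2 is also loosely worded.** An interval wholly above 15 mm does not contain 15 mm either. Reading it that literally raises the gate's pass rate from about 0.4% to 0.8% when every endpoint is at the margin and the correlation is 0.5, a small effect. Section 8.4.2 still decides on the interval, which 8.4.3 does not.
- **The gated 39% to 50% depends on a scenario.** It requires early success followed by a loss of effect at day 7. If the co-primaries are also at the margin, the gate protects. However, persistence beyond 24 hours is what the secondary endpoints examine, so that scenario matters.

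**Conclusion.** The concern holds: the secondary decision rule is wrong as written, although an upper-limit test was probably intended. The 50% against 2.5% at the margin, before the gate, depends on neither SD nor sample size. The disagreement band of about 6.9 to 15 mm assumes 48 per arm and an SD of 20 mm at the later visits. The gated 39% to 50% also assumes co-primaries truly at 2 mm and equal between-visit correlation of 0 to 0.9. The gate limits the harm only when the co-primaries fail too. This should be fixed before analysis.

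**What to change.** Replace the declaration sentence in 8.4.3 with: *Non-inferiority for a secondary endpoint is declared if the upper limit of the two-sided 95% CI for Vanish minus Clinpro, with change expressed as reduction from baseline, is below 15 mm, tested in the order of 5.3.2 and stopping at the first failure.*

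*Below* matches 8.4.2, where an interval whose limit equals 15 mm contains it. *Reduction* fixes the sign: the null in 8.1 describes an inferior Clinpro only if change means reduction.

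The cost is one sentence. Compared with the literal rule, the chance of a declaration per endpoint at a true 2 mm deficit, before the gate, falls from 99.9% to 88% (48 per arm, SD 20 mm), or to 85% with 43 per arm. If an upper-limit test was always intended, nothing is lost. The sample size and the co-primary analysis do not change.

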#### **8.4.4. Analysis of Additional/Exploratory Endpoints**

Ninety five percent (95%) confidence intervals will be generated for the difference between treatments in change from baseline using a Student's distribution at each evaluation time. No non-inferiority will be declared.

